## ABBREVIATIONS

AE	Adverse Event
BUN	Blood Urea Nitrogen
CBC	Complete Blood Count
DBS	Dried blood spot
IRB	Institutional Review Board
LC-MS/MS	Liquid Chromatography with tandem mass spectrometry
MOP	Manual of Procedures
PI	Principal Investigator
PO	per os/by mouth/orally
SAE	Serious Adverse Event
SOP	Standard Operating Procedure
TDM	Therapeutic drug monitoring

**STUDY SYNOPSIS**

Title	Single center, pilot evaluation of home-based therapeutic drug monitoring for tacrolimus and mycophenolate in kidney transplantation
Study Description	Part 1: Clinical validation of bioanalytical assay Part 2: Prospective, randomized, pilot evaluation of a text messaging intervention to facilitate self-collection of dried blood samples for tacrolimus and mycophenolate therapeutic drug monitoring
Study Duration	Part 1: 3 days Part 2: Enrollment duration: 3 months (up to 4 months if participating in qualitative interview) Subject follow-up duration: 0 months Overall study duration: 24 months
Study Center(s)	Single-center University of Michigan
Objectives	Evaluate tools to facilitate patient self-collection of samples for therapeutic drug monitoring of tacrolimus and mycophenolate including the self-collection device (Tasso-M20) and text messaging reminders.
Number of Subjects	Part 1: 45 (up to 90 if participants do not provide 2 sample, need to obtain 90 paired samples (Tasso vs. venipuncture) for appropriate statistical power) Part 2: 45
Disease/condition	Part 1: Solid organ transplant recipients requiring immunosuppression with tacrolimus and mycophenolate Part 2: Kidney transplantation requiring immunosuppression with tacrolimus and mycophenolate
Inclusion/Exclusion Criteria	See Section 3.0 for a complete list of inclusion and exclusion criteria
Description of Study Intervention:	Part 1: No intervention. Subjects will collect capillary samples using the Tasso-M20 and Mitra dried microsampling devices concurrently with their clinically indicated venipuncture. Part 2: All subjects will obtain self-collected dried blood spots for analysis of tacrolimus and mycophenolate using the Tasso-M20 device (Illustrated below). On two separate days approximately 6 weeks apart. Subjects will be randomized to two text messaging interventions to provide reminders and guide collection of samples in the home environment.

---

	
No changes will be made to the subjects' treatment based on data collected in this study. All changes to the medication regimen will be made at the treating provider's discretion.

Duration of Intervention	
Part 1: no intervention (sample collection duration up to 2 days)
 
Part 2: 3 months

Statistical Methodology	
Part 1: Bioanalytical method agreement will be assessed by Passing-Bablok regression and Bland-Altman plots.
 
Part 2: The primary outcome is successful to home collection of samples. Multivariable logistic regression will be used to identify participant characteristics associated with successful home collection.

Illustration of the Tasso-M20 dried blood samples collection kit (A) that includes self-placement on the upper arm (B) followed by activation (clicking the red button), timed collection (C), and automatic sealed storage of four samples in a cartridge (D) for bioanalysis

Illustration of the Mitra dried blood sample collection kit (A) that requires sampling from the capillary via fingerstick with the sample time for bioanalysis (B)

## STUDY SCHEMA

### Part 1:

Prior to  
Enrollment  
Study Day -14  
( $\pm$  14 days)

Total n=up to 90 (minimum of 50 samples): Obtain informed consent.

Visit 1  
Study Day 1

Collect paired dried blood (Tasso-M20 and Mitra) and venipuncture samples for tacrolimus and mycophenolate trough concentrations.  
Collect patient reported experience questionnaire

[figure not shown]
Visit 2  
Study Day 2  
( $\pm$ 7 days)

If patient remains hospitalized with a second 2nd standard of care tacrolimus trough ordered: Collect paired dried blood and venipuncture samples for tacrolimus and mycophenolate trough concentrations.  
Collect patient reported experience questionnaire (2nd day questionnaire may be obtained even if the patient does not have a second set of samples obtained)

## Part 2:

Prior to  
Enrollment  
Study Day -14  
( $\pm$  14 days)

Goal n=45: Obtain informed consent. Provide education on sample self-collection using Tasso-M20 device & text messaging. Collect baseline questionnaire data including medication adherence. Review medication list.

Self-collection 1  
Study Day 14  
( $\pm$ 14 days)

Administer text message intervention (beginning 48 hrs prior and ending 48 hours after).  
Patient collected dried blood samples at time 0, 1hr, 4hr, and 8hr  
Document collection times, medication doses in patient diary  
Mail samples to study site

Self-collection 2  
Study Day 56  
( $\pm$ 14 days)

Administer text message intervention (beginning 48 hrs prior and ending 48 hours after).  
Patient collected dried blood samples at time 0, 1hr, 4hr, and 8hr  
Document collection times, medication doses in patient diary  
Mail samples to study site

Visit 3  
(if applicable)  
Study Day 60  
( $\pm$ 28 days)

Purposive sampling (min N= 10)

Semi-structured qualitative  
interview

## 1.0 BACKGROUND AND RATIONALE

### 1.1 Background

Optimal immunosuppression therapy is critical for kidney transplantation success. The care of transplant recipients has improved remarkably over the last 50 years, and transplantation offers a clear survival benefit, higher quality of life, and lower cost than dialysis. Yet, 10-year all-cause graft failure remains high at approximately 50%. This number corresponds to many recipients requiring a second or third transplant, whereas, for others, it represents premature death from cardiovascular disease, infection, and malignancy. Importantly, the cause of negative transplant outcomes can often be traced in some capacity to immunosuppression, and optimization of the drug regimen has the potential to improve long-term graft and patient survival. New therapeutic options have failed to emerge, and the standard of care immunosuppression of tacrolimus and mycophenolate has not changed in nearly 20 years. Current practice is limited in its ability to balance the prevention of immune-mediated graft damage with the development of adverse side effects. Dose modifications remain reactive and primarily based on clinical evaluation and trough concentrations of tacrolimus, which does not adequately allow preemptive identification of patients at risk. As a result, precision pharmacotherapy, enhanced pharmacokinetic (PK) monitoring, and assessment of the alloimmune response are considered research priorities by both transplant professionals and patients.

These observations have led to the pursuit of expanded therapeutic drug monitoring (TDM) encompassing pharmacokinetic monitoring of drug exposure by estimating area under the concentration-time curve (AUC) for both tacrolimus and mycophenolate and evaluation of potential immune biomarkers. In several studies, estimating AUC has better correlated with reductions in acute rejection. Similarly, valganciclovir/ganciclovir, a commonly received antiviral, displays larger inter- and intra-patient PK variability. A reported 50 to 80% of patients do not achieve therapeutic exposure with current dosing recommendations. This is particularly relevant in kidney transplantation where low and fluctuating GFR is common in the post-operative period; subtherapeutic exposure is most common when adjusting the dose based on the current manufacturer recommendations for altered kidney function. Unfortunately, AUC is also the PK parameter associated with ganciclovir efficacy and toxicity. Additionally, relationships with several immune biomarkers (e.g., donor-derived cell-free DNA, NFAT-regulated gene expression) and outcomes have also been identified with evidence supporting use as pharmacodynamic markers. Monitoring concentrations of metabolites, such as mycophenolic acid glucuronide, may also be beneficial as they offer insight into metabolic capacity and are hypothesized to be associated with toxicity but are incompletely studied. Further knowledge of the impact of enhanced TDM remains needed to confirm optimal AUC targets and establish the best biomarker strategy to classify subclinical immune activity in large, prospective, longitudinal clinical trials. Finally, widespread implementation in practice is hampered by the perceived complexity compared to trough concentration monitoring. The full realization of the therapeutic potential will remain difficult in the absence of new tools to increase the translatability by reducing cost and patient burden.

### 1.2 Rationale

Forward progress in precision dosing using AUC and biomarker monitoring is hindered by the logistics of adequately powered, prospective studies. Home-based therapeutic drug monitoring (TDM) using volumetric dried blood microsampling to collect multiple concentration-time points for Bayesian AUC estimation and immune biomarker analysis is an innovative, practical, *and* cost-effective approach that could be used to implement precision dosing for both future studies and clinical practice.

Collection of dried capillary blood is a minimally invasive method for in-home use where patients self-collect small blood samples. Dried blood samples have been used for nearly a decade to obtain specimens for immunosuppression concentrations but can be limited by extraction recovery, hematocrit effect, and sample quality. Volumetric, whole sample analysis has the potential to mitigate these problems. Volumetric sampling has been used successfully to obtain immunosuppression and ganciclovir concentrations in several small studies. The next generation collection device, Tasso-M20 (Tasso Inc, Seattle WA), offers precise volumetric sampling with the potential to improve patient satisfaction and acceptability by offering a near painless experience but has not yet been used in transplantation. The device includes a self-contained lancet that obtains four 20  $\mu$ L dried capillary samples from the upper arm during a single, button-activated collection event (Figure 1).

In transplantation, existing literature suggests patients can collect dried blood samples at home, are generally satisfied with the procedure, and are willing to provide more samples with this method, particularly if it can replace venipuncture or reduce clinic visits. However, data are primarily limited to non-US populations and lack a robust framework to ensure a complete understanding of the behavior. Further, preliminary data shows that adherence to the collection is low, with 42-55% completion rates without intervention. Additional work is needed to develop strategies to increase adherence to monitoring. Text messaging reminders have been demonstrated to improve medication adherence and other positive health behaviors. Text messages are low cost with minimal infrastructure requirements and more accessible to patients with a low technology literacy or in rural areas with low cellular bandwidth. In a 2015 survey of kidney transplant recipients, 96% owned a mobile phone and 74% used text messaging compared to 47% who used apps. Text messaging is the preferred method of health communication in adolescent and young adult recipients. The use of text messaging offers the potential to be a viable tool to increase adherence to home-based TDM for most of the transplant population.

Our contributions are expected to develop a patient-centric strategy to allow frequent, longitudinal, minimally invasive sample collection for bioanalysis of immunosuppression and other supportive therapy drug concentrations. These contributions will be significant because they are expected to overcome many barriers that have limited progress towards enhanced precision pharmacotherapy in transplantation. The methods will facilitate decentralized multicenter clinical trials by reducing costs and simplifying biorepositories to achieve the sample sizes necessary to conclusively establish the benefits of expanded TDM on long-term patient outcomes. Further, improving the technical capacity of home-based sampling to substitute for frequent phlebotomy will improve patients' quality of life by allowing increased autonomy to self-monitor by collecting blood samples at home.

Figure 1.  
Tasso-M20 Device

## 2.0 STUDY DESIGN, OBJECTIVES AND OUTCOME MEASURES

This will be a single center, randomized, pilot evaluation of a text messaging intervention to facilitate self-collection of dried blood samples for tacrolimus, mycophenolate, and val/ganciclovir therapeutic drug monitoring. Participants are not required to be receiving val/ganciclovir for participation but the concentration will be analyzed if the drug is concomitantly being received by the participant under the direction of the treated clinical team.

### 2.1 Primary Objective (Part 2)

2.1.1 To compare the effect of bidirectional text communication on adherence to and accuracy of home-based AUC collection versus unidirectional text reminders in kidney transplant recipients receiving tacrolimus and mycophenolate.

**Primary Outcome Measure:** successful home-based TDM defined as the timely receipt of samples that are adequate for pharmacokinetic analysis.

### 2.2 Secondary Objectives (Part 1)

2.2.1 To assess the bioanalytical agreement of two sample collection methods (dried blood spot and venipuncture) as measured by Liquid Chromatography with tandem mass spectrometry (LC-MS/MS).

**Secondary Outcome Measure:** difference between drug concentrations measured from concurrent dried blood spot and venipuncture samples.

### 2.3 Exploratory Objectives

2.3.1 To evaluate the predictive performance of a mycophenolate matrix conversion equation. (Part 1)

**Exploratory Outcome Measure:** median percentage predictive error and median absolute predictive error

2.3.2 To assess the bioanalytical agreement of two sample collection methods (dried blood spot and venipuncture) as measured by LC-MS/MS assay at the University of Michigan PK Core and Michigan Medicine Clinical laboratory. (Part 1)

**Exploratory Outcome Measure:** difference between drug concentrations measured from the two LC-MS/MS assays.

2.3.3 To evaluate participant characteristics based on the Theoretical Domains Framework associated with successful home-based TDM. (Part 2)

**Exploratory Outcome Measure:** The relationship between patient characteristics and successful home-based TDM

2.3.4 To evaluate differences in participant reported experiences between the Tasso-M20 device and Mitra device (Part 1)

**Exploratory Outcome Measure:** difference between patient reported experience scores associated with the two sample collection devices

## **3.0 SUBJECT ELIGIBILITY**

Subjects must meet all of the selection criteria to be enrolled in the study. Study treatment may not begin until a subject has provided informed consent and meets the eligibility criteria.

Part 1:

### **3.1 Inclusion Criteria**

1. Recipient of a solid organ transplant
2. Male or Female adult ( $\geq 18$  years)
3. Receiving tacrolimus and mycophenolate
4. Ability to understand and willingness to sign a written informed consent

### **3.2 Exclusion Criteria**

1. Hemoglobin  $<8$  g/dL
2. History of allergy to tape adhesives

Part 2:

### **3.3 Inclusion Criteria**

1. Recipient of a kidney or kidney/pancreas transplant
2. Male or Female adult ( $\geq 18$  years)
3. Receiving immediate release tacrolimus and mycophenolate mofetil
4. Participant is willing to receive text notifications and has a mobile device capable of receiving texts
5. Ability to understand and willingness to sign a written informed consent.
6. Ability to understand, read, and speak English.

### **3.4 Exclusion Criteria**

1. Recipient of a multi-organ transplant (other than pancreas).
2. History of allergy to tape adhesives

Subjects may participate in both part 1 and part 2. Subjects participating in part 1 expressing interest in part 2 will be approached again once stable in the outpatient setting. Participants will sign separate consent for each part of the study.

## **4.0 SUBJECT SCREENING, ENROLMENT, AND RECRUITMENT**

A potential study subject who has been screened for the trial and who has signed the Informed Consent document will be initially documented on a Screening and Enrollment Log.

It is the responsibility of the investigator to determine subject eligibility prior to enrollment. After subject eligibility has been determined, a signed statement (i.e. eligibility checklist) by the investigator attesting eligibility will be included in the subject file. In addition, source documentation supporting each eligibility criteria will be placed within the subject file.

### **4.1 Subject Recruitment and Retention**

Part 1: Participants will be recruited from the inpatient transplant surgery service. Potentially eligible participants will be approached by the study team during admission to consider participation. For living donor transplant recipients, the study team may also approach potential participants during their History and Physical appointment typically scheduled 7-10 days before surgery.

Part 2: Participants will be recruited from the outpatient kidney transplant clinic at Michigan Medicine. Potentially eligible participants will be sent a letter describing the study and inviting the patient to contact the study team and/or the study team will contact participants via telephone if not attending clinic visits in person. The letter will be sent to the home address in a sealed envelope. Patients may also be approached during clinic visits to discuss the study. An incentive payment of \$20 will be provided for completion of each study visit or home collection (participants may receive a total of \$60). Patients may also be contacted via telephone to enhance retention if expected samples are not received.

Women and minorities will be recruited using the same strategy and are expected to be recruited at a rate consistent with their incidence in the transplant population at the University of Michigan.

### **4.2 Screen Failures**

For part 1: Screen failures are defined as participants who consent to participate in the clinical trial but do not subsequently have at least 1 set of paired samples obtained.

For part 2: Screen failures are defined as participants who consent to participate in the clinical trial but are not subsequently randomly assigned to the study intervention or entered in the study. A minimal set of screen failure information is required to ensure transparent reporting of screen failure participants, to meet the Consolidated Standards of

Reporting Trials (CONSORT) publishing requirements and to respond to queries from regulatory authorities. Minimal information includes demography, screen failure details, eligibility criteria, and any serious adverse event (SAE).

Individuals who do not meet the criteria for participation in this trial (screen failure) will not be rescreened. Screen failures will be replaced.

#### **4.3 Randomization**

Part 1: no randomization

Part 2: 45 patients who meet the inclusion criteria will be randomized in a 1:2 allocation ratio to receive one of two text messaging interventions stratified by age  $\geq$  or  $<$  65 years. The randomization list will be generated by the study biostatistician.

#### **4.4 Blinding**

Part 2: As subjects will be aware of the frequency and type of text messages received, blinding of patients is not possible. As a result, baseline data will be collected prior to randomization. Additionally, purposive sampling for qualitative interviews requires the investigator to be unblinded to study group.

### **5.0 INTERVENTION PLAN (PART 2 ONLY)**

#### **5.1 Intervention Administration**

All participants will self-collect dried blood samples using the Tasso-M20 device at the specified intervals. Each self-collection will obtain up to 80 $\mu$ L of capillary blood (4 x 20 $\mu$ L samples). Dried blood samples will be obtained concurrently with venipuncture samples at study visit 1 and 2. The participants will self-collect dried blood samples in their home environment for AUC analysis on two occasions. Self-collected samples will be collected immediately prior to the morning dose of tacrolimus and mycophenolate (C0) and at approximately 1, 4, and 8 hours after the dose.

To promote adherence and accurate sample collection, participants will be randomized to 1 of 2 automated text messaging interventions. Messages will be sent using a commercial web to text messaging gateway (Twilio). Twilio will be enabled in the REDCap project. Message replies will be stored in REDCap not on Twilio servers. The request inspector will be disabled in Twilio as required by REDCAP for HIPPA compliance. No protected health information (PHI) or identifying information will be in messages (See Table 1 for message content). A control group without messages will not be used due to preexisting knowledge of low rates of completion without intervention.

Anticipated sample collection dates and times will be discussed with the participant during the baseline visit to trigger messaging timeline. If a response is received to any message not using an expected keyword, the recipient will receive a text message that the entry is an invalid value and to try again. The participants will be educated to contact the study team with any issues.

The participant will be able to opt-out of messages with the standard keywords: “cancel”, “stop”, “end”, “quit”, “stopall”, and “unsubscribe.” In response they will receive the following message: “You have successfully been unsubscribed. You will not received any more messages from this number. Someone from the study team will contact you to follow up. Reply START to resubscribe.

In response to the keywords “help” or “info” participants will receive the following message: “For help, please call the study team [contact] or email [[contact]](mailto:[contact]).”

Upon completion of study visit 3 and all study blood sample collections, a subset of patients will be selected for semi-structured qualitative interviews to further explore the home-based TDM process. The interview guide is provided in Appendix C and is informed by the Theoretical Domains Framework mapped to the Capability-Opportunity-Motivation and Behavior system. Patients will be selected using maximum variation purposive sampling to capture multiple perspectives, including those demonstrating extremes in adherence, self-efficacy, diabetes status, and time post-transplant.

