### 7.1 Adverse Event Reporting Requirements

Since the responsibility of the management of the patient's transplant regimen is retained by the health care providers at the University of Michigan Transplant Center and not dictated by the study protocol, deaths and hospitalizations will typically not be study related. Serious adverse events (SAEs) and adverse events (AEs) that are related to the participant's kidney transplant or other chronic disease conditions are not unanticipated and therefore will not be considered reportable to the IRB. For the sake of our study purposes and outcomes we will track SAEs and AEs related to study participation.

Adverse event data will be reviewed by the project leadership team and will be summarized in reports quarterly. Non-serious (mild/moderate) adverse event data will be reported to the IRB in annual renewals. SAEs related to study participation will be reported to the IRB within 7 calendar days of identification by the study team. A privacy violation or breach of confidentiality will be reported to the IRB within 7 calendar days and to the Corporate Compliance office within 24 hours of identification.

Definition of Adverse Events (AEs): AEs that are of particular interest to our study and that we will specifically track include problems associated with capillary sampling (infection, bruising, and bleeding at the site of lancet puncture) and text message communication (privacy breach). Capillary sampling AEs will be assessed at 48 hours after collection via text message requesting patients to self-report (Table 1). We will also assess for hospitalizations, urgent care/emergency room visits, and death. These events will be collected via electronic record review or self-report.

The severity or grade of an adverse event may be measured using the following definitions:

Mild: Noticeable to the subject, but does not interfere with subject's expected daily activities, usually does not require additional therapy or intervention, dose reduction, or discontinuation of the study.

Moderate: Interferes with the subject's expected daily activities, may require some additional therapy or intervention but does not require discontinuation of the study.

Severe: Extremely limits the subject's daily activities and may require discontinuation of study therapy, and/or additional treatment or intervention to resolve.

The investigator or co-investigator is responsible for assignment of attribution.

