## **10. DATA AND SAFETY MONITORING**

As this study utilizes capillary blood sampling obtained via lancet (similar to monitoring done by patients undergoing self-monitoring of blood glucose) and reminder text messages with no PHI identifiers in conjunction with standard transplant management by the patients' established treating health care provider, this study is expected to pose no greater than minimal risk and therefore a data safety and monitoring board will not be used.

Participants will be asked about adverse events following sample collection as outlined previously. The text messages logs will be reviewed at the time of anticipated responses by the study team for complications requiring intervention.

The study team will meet at least quarterly to discuss matters related to:

- Enrollment rate relative to expectations, characteristics of participants
- Safety of study participants (Serious Adverse Event & Adverse Event reporting)
- Adherence to protocol (protocol deviations)
- Completeness, validity and integrity of study data
- Retention of study participants

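### The automatic reply to a non-keyword text says only that the entry is invalid; it should also give the study contact details, and log review should cover such texts whenever they arrive

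*Combined protocol and SAP*

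**What the plan says.** Four parts of the combined protocol and SAP bear on this.

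- **Section 5.1, automatic replies.** The trigger is stated broadly: "If a response is received to any message not using an expected keyword", then "the recipient will receive a text message that the entry is an invalid value and to try again". The next sentence adds a safeguard: "The participants will be educated to contact the study team with any issues". Sending help or info returns a message that begins "For help, please call the study team" and gives a telephone number and email. Sending an opt-out keyword returns a message promising that someone from the team will be in touch. On storage, the section says "Message replies will be stored in REDCap not on Twilio servers".
- **Section 7.1, adverse events.** Infection, bruising and bleeding at the puncture site are named as events the study will specifically track. "Capillary sampling AEs will be assessed at 48 hours after collection via text message requesting patients to self-report". Section 6.2 describes the same 48-hour question.
- **Section 10, monitoring.** "The text messages logs will be reviewed at the time of anticipated responses by the study team for complications requiring intervention". The team also meets at least quarterly, with participant safety on the agenda.
- **Study schema, Part 2.** For each home collection: "Administer text message intervention (beginning 48 hrs prior and ending 48 hours after" the collection). The collections are at Day 14 and Day 56, each with a window of 14 days either side.

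**The concern.** The text channel is the only prompted route described for finding lancet-site events at home, and the participants are immunosuppressed. A channel that asks about symptoms will sometimes be answered in sentences. Under the stated rule, such an answer draws an error message with no described pointer to a person. Section 5.1 already has both of the responses one would want: contact details for help or info, and staff follow-up for opting out. It gives neither to a non-keyword reply, which may be where a symptom is described.

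What is at stake is mainly prompt recognition of a problem and, secondarily, complete adverse-event counts. Nothing here touches the primary endpoint, the sample size or any treatment decision.

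**Working it through.** No sample-size or power figure is involved. The check sets the rules side by side for two kinds of message, then does the calendar arithmetic.

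**A. A non-keyword reply to a study prompt, such as a sentence in answer to the 48-hour safety question**
- Automatic error reply: yes, by section 5.1.
- Contact details in that reply: none described.
- Staff follow-up triggered by that reply: none described.
- Log review: due, because section 10 ties review to anticipated responses. Section 5.1 does not say whether entries rejected as invalid are stored with the other replies.

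**B. An unprompted or late text, sent outside a messaging window**
- Automatic error reply: unclear, because section 5.1 speaks of a response to a message.
- Log review: none described.

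**How long the periods without a described log review last**

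Inputs: collections at Day 14 and Day 56, windows of ±14 days (section 6.3), and messaging from 2 days before to 2 days after each collection (schema and section 6.3).

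Gap = (day of collection 2 − 2) − (day of collection 1 + 2).

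- Nominal: (56 − 2) − (14 + 2) = 54 − 16 = **38 days**.
- Shortest within the windows: (42 − 2) − (28 + 2) = 40 − 30 = 10 days.
- Longest within the windows: (70 − 2) − (0 + 2) = 68 − 2 = 66 days.

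The synopsis puts the collections about six weeks apart. At exactly 42 days apart the gap is 42 − 4 = 38 days wherever the windows fall. The 10 and 66 day figures need spacings of 42 − 28 = 14 and 70 − 0 = 70 days, so they are outer limits and not expected values.

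After collection 2 the last prompted safety question falls nominally on Day 56 + 2 = Day 58. No later log review is described; the next stated safety review is the team meeting, held at least quarterly.

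**The case against.** A reader might infer that a texted report of bleeding or infection is both turned away and left unseen for weeks. The documents do not support that for any single message. Message A gets the error text but arrives when log review is due. Message B may fall in the 38-day gap, but section 5.1 does not clearly apply the error reply to it. Nor does section 10 say that logs are read only at anticipated times; that is an inference from its being the only log review described.

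A reader might also infer that tracked adverse events are lost. That is not shown. The 48-hour question looks back over the period since sampling, so an earlier problem whose text was rejected is asked about again. Hospitalizations, urgent or emergency visits and deaths are collected by record review or self-report. Participants are taught to contact the team and remain under their transplant providers.

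Three further limits stand:

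- Table 1, which holds the message wording, was not available to check. The accepted keywords, and whether the safety question takes free text, are therefore unknown. For the same reason it cannot be said that no reply is expected between the 8-hour sample and the 48-hour question.
- Section 5.1 paraphrases the error message, so the real text may already carry contact details.
- The 38 days is a calendar interval and not a risk. Section 8.0 describes marks lasting 24 to 48 hours and rare slight bruising, so most of the gap lies after the period of likely trouble.

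These arguments remove the stronger readings. They do not explain why the stated error reply should omit contact details that the system already sends for other keywords, or who reads a text that arrives outside the expected times.

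**Conclusion.** The point holds as a minor safety and data-capture improvement. As written, section 5.1 can answer a participant's own description of a problem with nothing more than an invalid-entry message. Section 10 describes no reading of texts for a nominal 38 days between the two messaging windows, or after the safety question that follows collection 2. Existing safeguards limit the harm, and no event rate or count of affected participants can be derived from the documents.

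The conclusion assumes that the error message contains what section 5.1 describes and no more, and that section 10 lists all planned log review. If Table 1 already puts contact details in the error reply, only the log-review sentence is left to add.

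**What to change.** - **Section 5.1:** in both arms, have the error reply also carry the existing help wording with the study telephone and email. State whether entries rejected as invalid are stored.
- **Section 10:** extend log review to non-keyword replies whenever received. Use an automatic alert if the messaging system supports one. The documents do not say whether it does, so name a manual check as the alternative.
- **Section 7.1:** state that a lancet-site problem reported this way is recorded as an adverse event.

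The cost is a change of message wording and about one sentence in each of the three sections, with slightly longer error texts and some staff time spent on harmless replies. Using identical wording in both arms avoids adding a new difference between the two messaging interventions.
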